The study surveys will be conducted using web-based surveys, created using REDCap, which is supported by Northwestern University IT. We do not plan to share individual study results with subjects. However, aggregate data findings will be shared with home visiting programs.

17.0 Qualifications to Conduct Research and Resources Available:

Pregnant and postpartum women are the client base of home visiting programs, and are the intended recipients of our postpartum depression prevention intervention [name], the Principal Investigator, is an associate professor and nationally recognized expert in the fields of maternal depression and home visiting. For example, [name] is the lead faculty expert for a federally-funded Home Visiting Maternal Depression Collaborative Improvement and Innovation Network aimed at improving the ability of home visiting programs around the country to address maternal depression among their clients. This project builds on work he has conducted over the last 7 years integrating mental health services and interventions into home visiting. Alongside of [name], we also have three community stakeholders with strong relationships with the home visiting programs in the community, thereby enhancing the likelihood of this project's success.

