The study population consists of 1722 individuals. Of this total, 1680 will be HV clients, 24 will be home visitors, and 18 will be mental health professionals. The HV client study population consists of 1680 individuals recruited from 42 home visiting (HV) programs across Illinois and adjacent states. We will enroll these women as part of a randomized controlled trial, where 720 women will be enrolled at 18 HV programs randomized to Mothers and Babies group facilitation by paraprofessionals, 720 women will be enrolled at 18 HV programs randomized to Mothers and Babies group facilitation by mental health professionals, and 240 women from 6 HV programs will receive usual care home visiting services. The 42 HV programs participating in this project enroll clients via referrals from prenatal care clinics, Women, Infants, and Children (WIC) programs and other settings working with perinatal women; home visiting programs implementing the MB Course will implement five MB cohorts per site, over the course of the project. These women will be recruited \leq 33 weeks gestation upon referral.

Vulnerable Populations

Among our 1680 HV clients we are enrolling, we will enroll only pregnant women in this study, given that our Mothers and Babies Course is delivered prenatally as a postpartum depression prevention intervention. We will offer participation to prenatal home visiting clients, ages 16 and older, knowing the client base for home visiting programs includes pregnant teens. In many states these young women are considered emancipated minors. The Mothers and Babies Course has been used in home visiting programs and other prenatal care settings, with high ratings of acceptability and no ill effects detected. Please refer to the protections against risk description for study procedures in which observations of concern arise.

Study participants: We will work with 42 home visiting throughout the state of Illinois and adjacent states on this project. The population to be studied is pregnant women enrolling in HV programs \leq 33 weeks gestation upon referral, who are at-risk for major depression. Women \geq 16 years old enrolled in HV programs who are \leq 33 weeks gestation upon referral, will be eligible for enrollment; across the 42 HV programs ~80% of women receive a HV service \leq 33 weeks gestation, making them eligible for study participation.

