The post-intervention assessment consists of one depressive symptom measure, so no remuneration will be provided. Baseline and follow-up data will be collected and managed using REDCap (Research Electronic Data Capture), a secure web-based application designed to support data capture for research studies, hosted and supported by Northwestern’s Clinical and Translational Science Institute. Once research staff enters participant contact information, REDCap will generate emails or texts containing web-based survey links at scheduled time points. Baseline data will be collected within 2-3 weeks of establishing client eligibility and participation agreement. Women who do not complete the web-based baseline assessment in this timeframe will be contacted by phone by the Research Coordinator to complete the assessment either by phone or online, ensuring that baseline data are collected prior to the first MB group. Informed consent will be obtained prior to administering the baseline assessment. If a study participant decides that they do not want to consent to participate in this study, no data will be collected from this participant. For the post-intervention, 12-week postpartum, and 24-week postpartum assessments, study participants who do not complete web-based assessments within one week of the web link being sent to them will be contacted by the research team to complete the assessments by phone.

Table 4 describes this study’s outcome indicators, measures, and data collection timelines.

Outcome Indicator	Measure	Baseline	Post-Intervention	12 weeks postpartum	24 weeks postpartum
Depressive Symptoms	Edinburgh Postpartum Depression Scale	X			
Current & Lifetime Major Depressive Episode	Maternal Mood Screener (MMS)	X		X	X

DEPRESSION					
Depressive Symptoms*	Quick Inventory of Depressive	X	X	X	X
Symptomatology					
PROXIMAL OUTCOMES					
Behavioral Activation	Behavioral Activation	X		X	X
Pleasant Activities	Pleasant Activities Schedule	X		X	X
Mood Regulation	Negative Mood Regulation Scale	X		X	X
Social Support	MOS Social Support Survey	X		X	X
Decentering	Experiences Questionnaire	X		X	X
Relationship w/Partner	Dyadic Adjustment Scale	X		X	X
Responsive and Reactive Parenting	Parental Cognitions and Conduct toward the Infant Scale			X	X
Subjective Well-Being	Flourishing Scale	X		X	X
Perceived Stress	4-item Perceived Stress Scale	X		X	X
PRENATAL HEALTH BEHAVIORS					
DEMOGRAPHICS					
INTERVENTION SKILL USE					
INVOLVEMENT IN PRENATAL SERVICES					

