be conducted using online administration at the time of the first web-based survey. A preamble to the consent form will appear in REDCap on the screen prior to the participant reviewing the consent. This preamble will be an introduction to the consent form clearly explaining the participant's role as a research participant in the study. The preamble will read: "The purpose of this study is to learn how well the Mothers and Babies program* works to help pregnant women and new mothers manage stress and reduce depression, when delivered by different types of facilitators. We are asking you to take part in this research study because you are receiving services from a home visiting program or an early childhood program and you are in your 2nd or 3rd trimester of pregnancy. Your participation in this study will last approximately 6-12 months after you complete your first survey. You will be asked to complete surveys that ask about your mood, stress, social supports, and involvement in prenatal services. Surveys will take approximately 45 minutes to complete, and will be conducted at the beginning of the study, immediately following completion of the 6-week group sessions, 3-months after the birth of your child, and 6-months after the birth of your child. You can complete these surveys on the internet or by phone. You may also be asked to participate in a brief interview about your experience with the Mothers and Babies program. The interview will be conducted over the phone and will last approximately 30-60 minutes."

*The Mothers and Babies program intervention is described fully to the participant during the screening process prior to consenting into the research study. The preamble will be available in both English and Spanish.

A brief questionnaire will follow the consent form in order to ensure the participant understands that (1) their participation is voluntary, and (2) they may withdraw or refuse participation at any time without consequence to their home visiting services. Both the online consent form and the study surveys for home visiting clients will be available in English and Spanish. Each time a study participant fills out a survey, the survey will include a prompt to the participant asking if they wish to continue their participation by completing the next survey.

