Specific Aim #2 is to conduct a non-inferiority trial that compares the effectiveness of MB delivered by (a) mental health clinicians versus (b) paraprofessional home visitors.

Specific Aim #3 is to evaluate whether effectiveness of the two versions of MB (clinician led vs. paraprofessional home visitor led) varies according to patient characteristics (e.g., race, ethnicity, first-time mother, and/or geographic type of home visiting (HV) program (i.e., urban vs. rural).

Specific Aim #4 is to examine the feasibility and acceptability of MB delivered by paraprofessional home visitors and mental health clinicians.

Study time points include: baseline, immediately following the intervention period (or roughly eight weeks post enrollment for controls), 12 weeks postpartum, and 24 weeks postpartum. Primary time point of interest will be 24 weeks postpartum. This analysis plan will focus on the primary results manuscript, and thus, we will focus on Aims #1-#3.

Study Outcomes

Primary Outcome

Primary outcome of interest for Aims #1-#3 will be the Quick Inventory of Depressive Symptoms (QIDS-SR16) score as determined by participant self-report at 24 weeks postpartum. We will control for baseline QIDS-SR16 score. This is a continuous measure ranging from zero to 27 points, where higher scores signify increased depressive symptoms. QIDS-SR16 translates into depressive categories such that a score of less than five points indicates no depression, a score ranging from six to 10 indicates mild depression, 11-15 signifies moderate depression, 16-20

indicates severe depression, and anything above 20 would be labeled as very severe (<http://www.ids-qids.org/>). As a result, we deem a five-unit change or difference in score to be meaningful (as a jump in five points would result in an increase in depression severity tier for any individual patient).

Secondary Outcomes

The following secondary outcomes will further be examined in order to address subcomponents of specific aims and also to address some of the exploratory aims. These secondary outcomes align with key components of the Mothers and Babies intervention.

1. Incidence of major/clinical depression (major depressive episode [MDE])
 - a. A major depressive episode will be defined via the Maternal Mood Screener
 - b. MDE for the purposes of this study is defined as:
 - i. The participant indicates at least **five** of the problems listed within the past two weeks (part B on the form), **and**

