 - ii. **At least one** of the problems must be: symptom 1 (feeling depressed) or symptom 2 (losing interest or pleasure), **and**
 - iii. The participant indicates '**yes**' to the question: *Did these problems interfere with your life or activities a lot?*
2. Behavioral activation scale score (BA)
3. Social support (due to the highly skewed nature of this outcome, we dichotomized it into ≥ 4 versus <4).
4. Mood regulation
5. Decentering
6. Mental health service utilization (i.e., an indicator for whether participants are enrolled in therapy with a counselor and/or currently taking antidepressants). This outcome may be explored in greater detail in a separate paper; however, we plan to examine the difference between arms controlling for baseline mental health service utilization.

Tertiary Outcomes (the following will be explored in a separate paper from the primary results)

1. Pleasant activities
2. Perceived stress
3. Parental cognitions and conduct toward the infant scale
4. Dyadic adjustment scale
5. Flourishing scale
6. Prenatal health behaviors

The outcomes above are tied to validated scales with specific scoring requirements. The scoring instructions will be followed and analyses will proceed on the final, scored variables. In addition, we plan to summarize '**dosage**' of intervention in the active intervention arms as the number of sessions attended (out of six possible). We will also summarize the number of participants that were '**compliant**', which is defined as attending **at least four of the six sessions**.

Demographics and Baseline Assessments

The following are specific demographic/baseline assessments of interest for analyses. Primary analyses will adjust for these covariates as we anticipate they will influence outcome. We plan to report both adjusted and unadjusted intervention effect estimates:

1. Race/ethnicity (at the participant level): minority vs. not belonging to a minority category.
2. Whether participant is a first-time mother (i.e., current number of children = 0 at baseline).
3. Currently at risk for depressive episode (i.e., those NOT meeting criteria for MDE at baseline).

4. Primary language of intervention receipt (for MH and HV arms) or primary language in which the participant completed assessments (for control arm).
5. Education: at least some college vs. less than college.

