Analyses will proceed at the participant level. Primary analyses for QIDS-SR16 score at 24 weeks postpartum will involve all the participants in the study contributing data at this time point. Primary analyses will involve a linear mixed model for continuous outcome with independent fixed effect variables of baseline QIDS-SR16, study arm (three-level factor), and the baseline covariates listed above. We will report both covariate-adjusted and unadjusted estimates for intervention effect. Secondary analysis will be performed on those participants considered at risk at baseline (i.e., excluding the participants who do not meet the criteria for MDE as defined above). We plan to account for clustering effects via inclusion of a random site effect, which will allow for distinction of between and within-site variance. We will also explore inclusion of a random 'facilitator' effect as it is possible participants exposed to the same facilitator may have correlated responses. Intra-cluster correlation coefficients will be estimated via variance components estimates.

Intervention effect will first be evaluated via the adjusted Wald type III test for significant study arm effect at the 5% level of significance. If arm is significant at the 5% level, analyses evaluating the **superiority (Aim #1)** of HV-led intervention vs. control will proceed with Tukey's correction for multiple pairwise hypothesis tests. Assuming the Tukey-adjusted p-value for this comparison falls below the 5% level of significance in favor of the HV-led arm, **non-inferiority (Aim #2)** will further be assessed (using Tukey's correction) via pairwise comparison of adjusted 24-month QIDS in HV-led vs. MH-led arms. Figure 1 below depicts the margin and zone of non-inferiority for this comparison.

[figure not shown]

Figure 1. Margin of Non-inferiority (NI)

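### The baseline-to-endpoint interval varies from about 6 to 12 months, mostly with gestation at entry, yet recorded weeks' gestation is not in the adjusted primary model: a small, free improvement rather than a demonstrated bias

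*Protocol*

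**What the plan says.** **Entry and baseline.** The consent preamble (Protocol 8.0) addresses women on the basis that "you are in your 2nd or 3rd trimester of pregnancy". Protocol 3.0 sets the upper limit: women at or under "33 weeks gestation upon referral, will be eligible for enrollment". On the survey itself, Protocol 4.0 says "Baseline data will be collected within 2-3 weeks of establishing client eligibility and participation agreement". Protocol 7.0 expects the first MB group no more than four weeks after the recruitment call. All of these are timed from entry.

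**Endpoint.** In the SAP's paragraph on study time points, "Primary time point of interest will be 24 weeks postpartum". The consent preamble describes the last survey as "6-months after the birth of your child" and gives the total length: "Your participation in this study will last approximately 6-12 months after you complete your first survey". The endpoint is timed from birth.

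**Model.** The SAP's Statistical Methods section gives the primary linear mixed model "independent fixed effect variables of baseline QIDS-SR16, study arm (three-level factor), and the baseline covariates listed above", plus a random site effect. The list, under Demographics and Baseline Assessments, is race/ethnicity, first-time mother, MDE risk status, language, education and two indicators of mental health service use. The stated rationale is: "Primary analyses will adjust for these covariates as we anticipate they will influence outcome".

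**Gestation.** Weeks' gestation is a row in the baseline table shell. It is not in the covariate list, the variables to be summarized only, the three site-level balancing variables (Randomization Methods) or the Aim 3 effect modifiers (Statistical Methods).

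**The concern.** A woman who enters early in the second trimester has a baseline score nearly a year old at the endpoint, and MB lies several months further back than for a woman who enters near the referral limit. If QIDS-SR16 at 24 weeks postpartum depends on that gap, gestation at entry is prognostic. By the SAP's own rationale it is then a natural candidate for adjustment.

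Randomization gives it limited protection. Sites were allocated and women were then recruited within them. Gestation was not a balancing variable, and only six control sites contribute data. Gestation may also bear on missing data: the main analysis set is women with 24-week data, and early entrants have to be kept in the study for longer.

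At stake are some precision and the chance imbalance in gestation left in HV-led v control (Aim 1) and HV-led v MH-led (Aim 2).

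**Working it through.** **1. Reproduce the 6 to 12 months.** Interval = (gestation at birth − gestation at baseline) + 24 weeks, at 4.348 weeks per month. Gestation at birth is not in the documents; 37 to 40 weeks is assumed. The start of the second trimester is taken as 13 to 14 weeks. A referral at 33 weeks plus up to 3 weeks' delay puts the latest baseline at about 36 weeks.

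| Birth (weeks) | Baseline (weeks) | Interval (weeks) | Months |
|---|---|---|---|
| 40 | 13 | 27 + 24 = 51 | 11.7 |
| 40 | 14 | 26 + 24 = 50 | 11.5 |
| 40 | 33 | 7 + 24 = 31 | 7.1 |
| 40 | 36 | 4 + 24 = 28 | 6.4 |
| 37 | 36 | 1 + 24 = 25 | 5.7 |

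With 6 calendar months after birth in place of 24 weeks, the range is 6.2 to 12.2 months. The stated range is reproduced. Moving baseline from 14 to 33 weeks alone shifts the interval by 19 weeks; the survey delay and the date of delivery each account for about 3. The consent text does not say that gestation causes the range; that follows from this arithmetic. (Protocol 7.0 mentions 32 weeks for recruitment calls and 33 weeks at referral. These should be reconciled, but the result here does not depend on it.)

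**2. Chance imbalance in mean gestation.** Assumptions, none from the documents: entry spread evenly over 14 to 33 weeks, and a site ICC of 0.05 for gestation. From the SAP: 23 women per site for analysis (Power and Sample Size Considerations); 15 HV, 16 MH and 6 control sites (Randomization Methods).

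- SD = 19/√12 = 5.5 weeks.
- Variance factor per site = 0.05 + 0.95/23 = 0.0913.
- SE, HV v control = 5.5 × √[0.0913 × (1/15 + 1/6)] = 0.80 weeks; two SEs = 1.6 weeks.
- SE, HV v MH = 5.5 × √[0.0913 × (1/15 + 1/16)] = 0.60 weeks; two SEs = 1.2 weeks.

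**3. Shift in the arm difference.** Assumed slope: 0.05 to 0.10 QIDS-SR16 points per week.

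- HV v control: 1.6 × 0.05 = 0.08 to 1.6 × 0.10 = 0.16 points, or 1.6% to 3.2% of the 5-point meaningful difference.
- HV v MH: 1.2 × 0.05 = 0.06 to 1.2 × 0.10 = 0.12 points, or 3% to 6% of the 2-point margin.
- Slope of zero: no shift.

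**4. Precision.** Under the SAP's non-inferiority assumptions (16 sites per arm, 23 women per site, ICC 0.01, SD 6, two-sided level 5%/3), the effective n per arm is 368/(1 + 22 × 0.01) = 301.6. Power for 2 points is 95.5%, consistent with the SAP's claim of over 90%. If gestation had a partial correlation r with the outcome (r assumed), the SD would become 6 × √(1 − r²):

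- r = 0.05: residual variance falls by 0.25%, power 95.6%.
- r = 0.30: residual variance falls by 9%, power 97.1%.

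**The case against.** The case against making more of this is strong, and most of it stands.

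- **Systematic difference by arm.** A reader might infer that MB sites, which have groups to fill, enroll women at different gestations from control sites. The documents do not support this. Protocol 7.0 plans 40 women per program in five cohorts, each recruited over about a month, at all 42 programs including controls. The referral limit and the research team's contact procedures do not differ by arm. For HV v MH, both arms fill groups. A systematic gap of, say, 3 weeks would give 3 × 0.05 = 0.15 to 3 × 0.10 = 0.30 points, but nothing in the documents points to such a gap.
- **Chance imbalance as bias.** Sites are randomized and the model has a random site effect, so the effect of gestation on the outcome is already part of the variance components and the confidence interval. Omitting a prognostic covariate costs precision; it does not make the test invalid.
- **Age of the baseline score.** A reader might argue that baseline QIDS-SR16 should count for less when it is older, and that adding gestation corrects this. A main effect does not: it leaves one common baseline slope for all women. Only a baseline-by-gestation interaction would change that, so this is not a reason for the change proposed here.
- **Adequacy of the existing plan.** The SAP pre-specifies a reasoned covariate set with baseline QIDS-SR16 and MDE status, reports adjusted and unadjusted estimates, and tabulates gestation by arm, so an imbalance would be seen. Time since birth at the endpoint is nominally the same for every woman.

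What remains is narrower. A recorded baseline variable that drives most of a roughly twofold spread in the interval can be adjusted for at almost no cost. An imbalance first noticed in the baseline table could prompt adjustment only after the fact.

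**Conclusion.** The facts hold: the interval runs from about 6 to 12 months, gestation at entry produces most of that spread, and weeks' gestation is planned for the baseline table but not for the adjusted primary model. This is an omission from the adjustment set, not a contradiction, a wrong figure or a demonstrated bias.

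The likely size is small. The shifts in working step 3 rest on the assumed entry distribution, gestation ICC and slope, none of which the documents give. The precision gain rests on an assumed correlation. No conclusion or power figure in the plan is shown to change. The point is an optional improvement whose true benefit cannot be quantified from the documents.

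**What to change.** Before database lock, add weeks' gestation at baseline, as a continuous variable, to the covariate list in the SAP's Demographics and Baseline Assessments section. It then enters the adjusted primary model through the existing wording of Statistical Methods. Name it also in the multiple-imputation model under Analytic Dataset, where the SAP does not list the imputation variables.

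Use gestation at baseline, not the realized interval from baseline to endpoint. The realized interval depends on the delivery date, which falls after randomization.

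The cost is one line in the SAP and one degree of freedom, with no new data. The SAP's Technical Details section already provides for documented modifications, and Timeline for Analyses rules out formal analyses before lock. A change made before then is pre-specified; made later, it could look data-driven.
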